### *1. Safety*

Adverse events are expected to have a Poisson or negative binomial distribution. The distribution will be examined and the appropriate regression models will be used to compare counts of serious adverse events between conditions. Logistic regression will be used to compare binary adverse events (e.g. death). Risk ratios will be adjusted as per primary analysis with age, and mRS included as covariates.

### *2. Demographics*

Baseline demographic characteristics will be tabulated. Between condition differences in continuous/ordinal measures will be assessed using one-way ANOVA or the Kruskal-Wallis test. Chi-square tests will be used to assess differences in categorical variables.

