## **8 Site Randomisation**

Sites will be randomised at the beginning of the project to determine the sequencing of the introduction of the intervention period.

It is anticipated that numbers of participants recruited in metropolitan sites may be higher than in regional sites due to potential transfer of patients to tertiary metropolitan hospitals for early treatment post injury. In order to minimise potential differences in participant numbers across steps in the wedge, one metropolitan and one regional site (cluster) will be paired prior to randomisation, then these pairs of sites will be randomised. Sites will be assigned to a particular intervention commencement time through the use of computer-generated sequence of random numbers. The process will allocate sites to one of four commencement periods (see Figure 1).

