### **16.3 Sample Size**

Sample size was estimated using GPower 3.1, and adjusted for the design effect of the stepped-wedge design using the method described in Woertman et al. Based on the literature, the mean difference between stroke and non-stroke populations on the Euro QOL–5D VAS is approximately 25 points with a standard deviation of 25. We anticipate that the intervention will result in an improvement of 15 points on the Euro QOL–5D VAS (with a standard deviation 25). This equates to a medium-large effect size of  $d=0.6$ . GPower estimated that we would require a total of 90 participants to detect this difference with 80% power at the 5% significance level. To adjust for the design effect, we assumed a conservative intraclass correlation of 0.08. After adjusting for the design effect for a 4-step stepped-wedge design with one baseline measurement and one follow-up measurement, we estimate that we will need to recruit 13 patients at each site in every time period. This equates to a total sample size of 312 patients.

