#### **16.4.1 Primary outcome analysis**

The primary hypothesis (H1) will be analysed using a mixed effects linear regression model, which controls for the effects of secular trends over time. The model will be designed to assess the effect of the intervention on Euro QOL–5D-3L VAS score at 26 weeks post injury. Differences in baseline characteristics will be included in the model.

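### The baseline tests ignore hospital and period, so in this stepped wedge they reject above their nominal 5% (about 1.5 to 3 times at an assumed ICC of 0.08) without any selective recruitment

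*Protocol*

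**What the plan says.** Protocol Section 16.4.2, item 2 (Demographics) tabulates baseline characteristics and then tests them: "Between condition differences in continuous/ordinal measures will be assessed using one-way ANOVA or the Kruskal-Wallis test". For the rest, "Chi-square tests will be used to assess differences in categorical variables". No hospital or period term is mentioned.

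Section 8 pairs each metropolitan site with a regional site, and then "these pairs of sites will be randomised". Under the Synopsis and Section 5, two sites cross over every 26 weeks after an initial 26-week control period. Figure 1 shows six data-collection periods. Section 11 puts time on intervention at 1 to 2.5 years depending on the site.

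Section 16.4.1 controls the primary model for secular trend and adds: "Differences in baseline characteristics will be included in the model". In Section 16.4.2 the models for processes of care, occasions of service, carer strain, and anxiety and depression each have a time effect and a random site effect.

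**The concern.** One-way ANOVA, Kruskal-Wallis and chi-square judge a difference between conditions against the variation expected if all patients were independent and exchangeable. Here condition is tied to hospital and to calendar time. Control patients come mainly from late-crossing pairs and early periods; intervention patients come mainly from early-crossing pairs and late periods. Any stable case-mix difference between hospitals, or any drift over time, therefore pushes the tests above 5% even when recruitment is identical under both conditions.

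The protocol gives reason to expect such variation. Section 5 cites very different local contexts and possible clinical change during the trial, and baseline variables such as language group and residence location (Section 10.2.1) depend on geography. The outcome models allow for this; the baseline tests do not.

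Two things are at stake. Patients are recruited after sites are randomised (Sections 8 and 9), and most investigators cannot be blinded to phase (Section 16.4.2, item 3), so selective recruitment is a real possibility. A significant baseline difference under these tests could not be attributed to it. The sentence quoted from Section 16.4.1 may also bring the flagged differences into the primary model.

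**Working it through.** **1. Reproduce the plan's sample size.** Section 16.3 states: "GPower estimated that we would require a total of 90 participants to detect this difference with 80% power at the 5% significance level". A two-sample t test with d = 15/25 = 0.6, two-sided 5% and 80% power needs 44.6, so 45 per arm, or 90. The same section says "we assumed a conservative intraclass correlation of 0.08". With ICC 0.08, four steps, one baseline and one follow-up measurement and n = 13, the stepped-wedge design effect is

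(1 + 0.08 × 64)/(1 + 0.08 × 38) × 3 × 0.92/(2 × 3.75) = (6.12/4.04) × 0.368 = 0.557.

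Then 90 × 0.557 = 50.2 per period, and 50.2/4 = 12.5, so 13. The total is 13 × 4 pairs × 6 periods = 312. The text says "we estimate that we will need to recruit 13 patients at each site in every time period", but 13 at each of eight sites over six periods would be 624. The stated 312 corresponds to 13 per pair and period, which is used below.

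**2. Mix of the two conditions.** Pair k is in control for k of the six periods. That gives 1 + 2 + 3 + 4 = 10 control and 5 + 4 + 3 + 2 = 14 intervention pair-periods, or 130 and 182 patients.

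| Pair | Share of control | Share of intervention | Difference w |
|---|---|---|---|
| 1 | 10% | 35.7% | 0.257 |
| 2 | 20% | 28.6% | 0.086 |
| 3 | 30% | 21.4% | -0.086 |
| 4 | 40% | 14.3% | -0.257 |

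The sum of w² is 0.147. Numbering periods 0 to 5, the mean period is 10/10 = 1.0 for control and 50/14 = 3.57 for intervention. The gap is 2.57 × 26 = about 67 weeks.

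**3. Variance of the pooled difference**, with no selection, no drift and total variance 1:

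- Assumed by the tests: 1/130 + 1/182 = 0.0132.
- Actual, clustering at pair level: ICC × 0.147 + (1 - ICC) × 0.0132. At 0.08 this is 0.01176 + 0.01213 = 0.0239, a ratio of 1.81. The rejection rate is P(|Z| > 1.96/√1.81) = 14.5%.
- Actual, clustering at site level with two equal sites per pair: the sum of w² halves to 0.0735. At 0.08 this is 0.00588 + 0.01213 = 0.0180, a ratio of 1.37 and a rejection rate of 9.4%.

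**4. Simulation**, N = 312, 5,000 runs per row, no selection and no drift. Chi-square is on a median split.

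| ICC (assumed) | Cluster | Analytic | ANOVA | Kruskal-Wallis | Chi-square |
|---|---|---|---|---|---|
| 0.02 | pair | 7.4% | 6.9% | 6.8% | 6.4% |
| 0.02 | site | 6.1% | 6.7% | 6.5% | 5.8% |
| 0.05 | pair | 11.0% | 9.9% | 9.8% | 8.0% |
| 0.05 | site | 7.7% | 7.6% | 7.5% | 6.9% |
| 0.08 | pair | 14.5% | 15.5% | 15.5% | 11.7% |
| 0.08 | site | 9.4% | 9.3% | 9.1% | 8.0% |
| 0.15 | pair | 21.7% | 22.9% | 22.8% | 17.3% |
| 0.15 | site | 13.1% | 13.5% | 13.3% | 10.8% |

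Further chi-square runs at ICC 0.08, including binary prevalences of 15-50%, gave 8.7-11.0% at pair level and 7.1-8.1% at site level. With ICC 0 and no drift, all three tests hold about 5%.

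**5. Drift, as illustration only.** The documents give no case-mix trend. An assumed 0.05 SD per period shifts the difference by 2.57 × 0.05 = 0.129 SD, or 0.129/√0.0132 = 1.12 standard errors. That gives about 20% rejection with no clustering. Simulation gave 20%, and 25-27% with ICC 0.08.

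**6. Comparison with terms for cluster and period.** In the same simulations, a linear model with cluster and period fixed effects rejected 4.4-6.3% of the time.

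**The case against.** Four objections carry weight.

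- **The size is conditional.** The 0.08 is the VAS assumption, and no ICC is given for any baseline characteristic. The clustering level is also open: Section 5 makes pairs the clusters, the Synopsis makes individual sites the clusters, and the secondary models use a site effect. Each pair mixes a metropolitan and a regional hospital, so much of the variation may lie within pairs, where it inflates less. This stands. A reader might infer that all three tests flag imbalance at three times the nominal rate. That holds only for ANOVA and Kruskal-Wallis with pair-level clustering at 0.08. Chi-square, which would apply to most of the variables in Section 10.2.1, is less inflated, so multiplying the ANOVA rate across every baseline variable would overcount false flags.
- **Item 2 does not say that the tests check for recruitment bias.** If hospital mix makes the groups differ, they do differ, and reporting so is fair description. Calling these tests the trial's main evidence on recruitment bias would be inference. But the table already serves description. A p-value adds a reference to chance under independent sampling, which this design rules out.
- **Section 16.4.1 does not say that significance tests choose the covariates.** A reader might infer that they do. The wording permits that reading without stating it.
- **No effect on the primary estimate is shown.** No bias, error rate or power for H1 was computed, and the primary model already controls for secular trend. This also stands.

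**Conclusion.** The point holds as a fault in tests that the protocol names, so it is not a detail left to a later analysis plan. With any between-hospital variation or calendar drift, the tests of item 2 use too small a variance or a wrong reference value, and they reject above 5% with no selective recruitment.

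At an assumed ICC of 0.08, N = 312 and no drift, the inflation is roughly 1.5 to 3 times nominal, depending on test and clustering level. For ANOVA it is about 6-7% at ICC 0.02 and 13-23% at 0.15. Drift would add to this by an amount that the documents do not allow one to fix.

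The consequence is limited. The baseline p-values cannot be interpreted as evidence for or against selective recruitment, and they should not feed the primary model. The point does not by itself invalidate the analysis of H1.

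**What to change.** In Section 16.4.2, item 2:

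- Delete the ANOVA, Kruskal-Wallis and chi-square tests.
- Tabulate baseline characteristics by condition, and by pair and period, with standardised differences.
- If a check on recruitment is wanted, estimate the condition effect on each key characteristic from a model with period fixed effects and pair and site terms. Report it with its 95% interval.
- State, with matching wording in Section 16.4.1, that these results do not choose covariates for the primary model.

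The cost is a change of wording and a slightly larger table; no new data are needed and the sample size is unaffected. Intervals will be wider than the pooled tests imply, because they reflect the clustering. With so few clusters, a model with random pair and site effects may be unstable. A 300-run check of that form held about 5% but gave many convergence warnings. Fixed cluster terms, as in step 6 of the working, are a workable alternative.

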### *3. Blinding*

All assessors will be independent of the researchers involved in the intervention or the trial. However, assessors in rural areas will most likely be aware of whether their local hospital is in intervention or control phase. Therefore it is not possible to blind the assessors, patients or most investigators on whether the patients received intervention or not. However, follow-up assessors will be blinded to the baseline assessment of any given participant. All analyses will be carried out by a statistician who is blinded to the randomization of sites and allocation of individual patients to intervention or control. Assessor blinding will be examined according to CONSORT guidelines at 12 weeks. The James blinding index will be used to assess the effectiveness of the blinding.

### *4. Post hoc analyses*

The relationship between amount of services received, baseline stroke and traumatic brain injury severity and recovery are likely to be part of post hoc analyses given their clinical relevance.

### *5. Interim analyses*

The DSMC will review interim data for adverse events and serious adverse events. The DSMC will use the Haybittle-Peto boundary with a difference of at least 3 standard errors in the analysis of serious adverse events (e.g. death

from all causes, aspiration pneumonia within the first 50 days post injury) needed to justify halting, or modifying the study before the planned completed recruitment. There will be no interim analyses for efficacy.

## 16.5 Economic Analysis

The economic analyses will provide important evidence in facilitating translation of this research into practice and policy. Very little economic evidence exists related to rehabilitation services post stroke or traumatic brain injury. **Reliable evidence to drive redistribution of scarce healthcare resources to accommodate the service delivery gap** in meeting Aboriginal health needs following brain injury is urgently needed.

Cost description analyses of each comparator group will be detailed using a decision-analytic model. All costs will be valued in 2020 dollars. Where prices in 2020 are unavailable, adjustment to the real price will be made using the published health sector specific deflator/inflators. Intervention delivery costs will also be accounted for as part of the intervention group. The incremental costs and benefits of the intervention (i.e. Quality Adjusted Life Years [QALYs] gained derived from EQ5D results) compared to control will be determined and expressed as a ratio by dividing by the net benefits for the outcomes of interest. Sensitivity and uncertainty (probabilistic multivariable [Monte-Carlo simulated]) analyses to account for variability in point estimates will be performed to assess the robustness of results. The intervention will be judged cost-effective if the incremental cost per QALY gained is <\$50,000 (i.e., the willingness-to-pay threshold). Cost-effectiveness Acceptability Curves will also be generated to provide a plot of the probability that the intervention is cost-effective as a function of willingness to pay. This method provides a measure of magnitude and uncertainty of cost-effectiveness, expressed as a probability statement meaningful to policy makers.

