## 5 Study Design

**Design:** A stepped wedge cluster randomised control trial (CRCT) design will be used, with pairs of healthcare sites functioning as clusters. Each metropolitan hospital will be paired with a regional hospital. The pairing will be broadly based on existing stroke pathways linking the hospitals. Twenty-six weeks of baseline control data will be obtained prior to implementation of the intervention, which will be introduced sequentially to all sites at 26-week intervals. Control data will continue to be collected at each site until the intervention commences. The intervention will continue within each cluster until the last clusters have received the intervention for a 52 week period.

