Resource utilisation information will be used to estimate the cost effectiveness of both the cultural training and the implementation of the ABIC (see section 12.5). In brief, cost description analyses of each comparator group to 26 weeks will be detailed. Cost items will be valued for the reference year 2020. Where prices in 2020 are unavailable, adjustment to the real price will be made using the published health sector specific deflator/inflators. Incremental cost-effectiveness ratios or the net difference in costs and outcomes will be calculated for the intervention group relative to the control group. Sensitivity and uncertainty (probabilistic multivariable [Monte-Carlo simulated])

analyses to account for variability in point estimates will be performed to assess the robustness of results.

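### The H5 cost-effectiveness increment is defined as a group difference against a $50,000/QALY rule, without the calendar-time and cluster terms stated for other outcomes

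*Protocol*

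**What the plan says.** The economic analysis is described in two places in the protocol. Section 10.5 says: "Incremental cost-effectiveness ratios or the net difference in costs and outcomes will be calculated for the intervention group relative to the control group". Section 16.5 says: "The incremental costs and benefits of the intervention (i.e. Quality Adjusted Life Years [QALYs] gained derived from EQ5D results) compared to control will be determined", expresses this as a ratio, and adds a decision rule: "The intervention will be judged cost-effective if the incremental cost per QALY gained is" below $50,000. Costs of each comparator group are to be described with a decision-analytic model. The only step related to time is pricing: "All costs will be valued in 2020 dollars", with health-sector deflators or inflators. On uncertainty the text reads: "Sensitivity and uncertainty (probabilistic multivariable [Monte-Carlo simulated]) analyses to account for variability in point estimates will be performed to assess the robustness of results". Acceptability curves follow. Neither section mentions calendar period or clustering.

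The effectiveness analyses are described differently. Section 16.4.1 says: "The primary hypothesis (H1) will be analysed using a mixed effects linear regression model, which controls for the effects of secular trends over time". Section 16.4.2 gives time as a fixed effect and site as a random effect for H2 and for both H4 outcomes. The H3 model mentions within-cluster effects but no calendar-time term.

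On the design, section 5 makes four metropolitan-regional pairs the clusters, which cross over at 26-week steps. The last cluster receives 52 weeks of intervention, and "Control data will continue to be collected at each site until the intervention commences".

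**The concern.** In a stepped wedge the treatment label is tied to calendar time: early participants are mostly controls and late participants mostly receive the intervention. A plain difference between the two groups mixes the intervention effect with whatever changed over the trial. The protocol expects such change. Section 5 names changes of staff and of local service organisation, and section 11.1.1 provides for hospital quarantine under COVID-19. On the Figure 1 dates, January to June 2020 falls when every cluster is already in its intervention phase.

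There is also a mismatch within the plan. Section 16.4.2 models occasions of allied health service with a time term. Section 10.5 costs allied health sessions for H5, but describes their comparison only as a group difference.

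Objective 3 is a business case for funding, and H5 carries a numeric decision rule. Drift in length of stay, transfers, outpatient use or utility could move the ratio across that line with no change in what the intervention does.

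**Working it through.** **Layout.** Inputs: 4 pairs, 26-week steps, first period all control, last cluster with 52 weeks of intervention (section 5); intervention lengths from 2.5 years down to 1 year (section 11); 13 per cell and a total of 312 (section 16.3). The plan's total reproduces with 13 per pair per period: 4 × 6 × 13 = 312.

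- Control cells by pair: 1 + 2 + 3 + 4 = 10, or 130 participants.
- Intervention cells by pair: 5 + 4 + 3 + 2 = 14, or 182 participants.
- Sum of period numbers over control cells: 1 + 3 + 6 + 10 = 20, mean 20/10 = 2.00.
- Sum over intervention cells: 4 × 21 − 20 = 64, mean 64/14 = 4.57.
- Gap: 2.57 periods × 26 weeks = 66.9 weeks.
- Periods 5 and 6 hold no controls: 8 of 14 intervention cells, or 104 of 182 planned participants.

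**Bias of a group difference.** With zero true effect and a linear drift of δ per period shared by all clusters, the difference in group means is (4.57 − 2.00) × δ = 2.57δ. Passing the same drift through a model with period and cluster terms gives 0.00.

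**Illustrative size.** The protocol gives no drift, QALY gain or expected ratio, so every input here is an assumption.

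- Cost drift of $200, $500 or $1,000 per period biases incremental cost by $514, $1,286 or $2,571. Divided by an assumed gain of 0.03 QALY, the ratio shifts by about $17,000, $43,000 or $86,000 per QALY. Falling costs shift it the other way.
- Utility drift of 0.005, 0.01 or 0.02 per period, applied over the half year, adds 2.57 × drift × 0.5 = 0.0064, 0.0129 or 0.0257 QALY. With no cost drift, an assumed true $75,000 per QALY ($1,500 / 0.02) would read about $56,800, $45,700 or $32,800.
- With utility falling by 0.005 or 0.01 per period, an assumed true $40,000 per QALY ($800 / 0.02) would read about $58,900 or $112,000.

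**Clustering.** The intraclass correlation of 0.08 is the plan's value for the VAS (section 16.3). None is given for costs or QALYs. In units of total variance:

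- Each pair's weight in the group difference is (intervention cells)/14 − (control cells)/10: 0.257, 0.086, −0.086, −0.257. The squares sum to 0.147.
- Variance with clustering: 0.08 × 0.147 + 0.92 × (1/182 + 1/130) = 0.0239.
- Variance ignoring clustering: 1/182 + 1/130 = 0.0132.
- Ratio 1.81, so the standard error is understated by √1.81 = 1.35. At the plan's SD of 25 this is 2.87 against 3.86 VAS points.

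**The case against.** The strongest reply is that neither section says participants are pooled or that the comparison is unadjusted. An incremental ratio is always intervention relative to control. H1, H2 and H4 are also worded as comparisons with usual care, and all three have time-adjusted models. Covariates for cost and QALY regressions, and the source of the Monte-Carlo distributions, often sit in an analysis plan or a health-economic plan that is not shown. Section 10.5 also presents its account as brief.

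Much of this stands. A reader might infer that the protocol prescribes a crude pooled contrast, but the text does not say so. Four further inferences are not supported:

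- That drift would be credited to the intervention. Its direction is unknown and it could equally count against the intervention.
- That the acceptability curve is too certain. That follows only if its inputs ignore clustering, which is not stated.
- That the problem can be expressed as a false-positive rate. H5 has no significance test.
- That a disagreement between H1 and H5 would reveal the missing adjustment. H1 uses the VAS, while H5 uses EQ-5D-derived QALYs and costs, so the two can differ under identical adjustment.

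The objection does not remove the point. For H1, H2 and H4 the comparator wording is followed by a stated time-adjusted model. For H5 it is followed only by a group difference and a fixed threshold. Section 10.5 refers the reader to section 12.5, but section 12 ends at 12.3.

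**Conclusion.** The point holds in conditional form. Sections 10.5 and 16.5 define the H5 increment as a group difference and attach a $50,000 per QALY decision to it, without the secular-trend control stated for H1, H2 and H4 or the site random effect stated for H2 and H4. Followed as written, the increment would include 2.57 times any per-period drift in service use or utility, in either direction. Pricing in 2020 dollars removes price inflation but not changes in volume, case mix or utility.

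The 2.57-period gap rests on the planned layout with equal cells. The 1.35-fold understatement of the standard error applies only if clustering is ignored, and borrows the VAS intraclass correlation. The dollar and ratio shifts are illustrations on assumed drifts and QALY gains. They show that the threshold could be crossed either way, not that it will be.

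**What to change.** In sections 10.5 and 16.5, state that the incremental costs and incremental QALYs entering the decision-analytic model will be estimated from models with a fixed effect for calendar period and a random effect for cluster, as section 16.4.2 already does for H2 and H4 with time and site. Name the cluster level, because section 5 calls the pairs clusters while section 16.4.2 uses site. State also that the Monte-Carlo analysis and the acceptability curve will use uncertainty that preserves clustering.

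The cost is wording, slightly more analysis and wider intervals. As a guide on the VAS scale (ICC 0.08, SD 25), the standard error from a model with period effects and a pair random effect is 4.99, against 3.86 for a group difference whose error allows for clustering. No new data are needed: control and intervention periods are recorded by site (section 5.1), and participants are analysed under their recruiting site (section 16.4).
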